A novel, technology-supported developmental coach service delivery model will be developed and tested. Importantly, the model will be responsive to the knowledge needs of families and service needs of children at high risk for new disabilities. Resulting service delivery models will empower families, will be effective, efficient and scalable across metro, urban and rural settings nationally, and will be associated with cost-savings to the system and patient/family benefits to health and well-being.

Research question: To evaluate the feasibility and the effectiveness (changes in parent health, developmental service utilization and cost-effectiveness) of a self-management intervention (including health coach, online education tools and support network), when compared to usual care in service delivery practices, for parents of preschool children with elevated risk of BDD prior to school entry.

PROJECT DESCRIPTION

RATIONALE

Children with, or at elevated risk for, brain-based developmental disabilities (BDD) experience chronic lifelong functional consequences with new challenges emerging at each stage of development. In the preschool years (3-6 years), needs arise from vulnerabilities linked to critical and newly emerging cognitive, speech, motor, behavioural and social skills [1, 2]. For families, this can be a stressful period as they witness their child's differences and await assistance to organize services and coordinate care, and must consider the best options in preparation for school entry. Nationally and internationally, service delivery models during this critical period are not standardized [3], and differ within and across provinces and across patient conditions, leading to long wait times, service gaps and duplications [4, 5].

Recently, a focus on care coordination (e.g. care planning, navigating healthcare system) has emerged in the literature for those with chronic disease [6]. At the same time, science has emerged demonstrating how patient education programs that promote self-management for those with specific chronic conditions have positive effects on health behaviours, improved health status, and decreased health care costs [7]. Health coaching research to date has, for the most part, focussed on improving motivation and adherence to health behaviours and to support lifestyle change in order to prevent the negative course of a disease [8]. Health coaching is tailored to the patients' knowledge needs, and can be delivered through many means – one to one or via telephone or technology [9].

The preschool years are a time of stress for families as their preschool child awaits assessment, or even as they receive services for brain-based disorders. Similarly, the system and society struggle to meet needs of families in a timely and appropriate manner in the face of escalating costs. Given these struggles, there is need to examine whether a health-coach style of intervention coupled with parent education delivered through an online platform can be effective in empowering families, by delivering information, providing social (parent to parent) supports, and decreasing demand on health and developmental services. This innovation provides a significant service re-design in a system at critical point of transition.

AIMS AND HYPOTHESES

Primary Hypotheses:

- (1) A standardized approach to “developmental coaching” (i.e. coach + online education tools + peer support network) is *feasible* in the real-life context and *acceptable* to mothers and fathers and can be delivered across multiple inter-provincial sites that recruit patients from urban/suburban/rural settings.
- (2) A standardized approach to “developmental coaching” enhances *parental health* (parents' empowerment and sense of competence, quality of life, and minimizes parenting stress), *family health care experience* (care coordination experience and process of care) at similar *health care cost* (economic analysis), when compared to usual care.

Secondary Hypotheses:

- (3) Given the differences that exist in caregiver burden, Fathers will contact the coach and use the online platform less frequently than mothers. (*sex/gender hypothesis*)
- (4) Parents will use the online platform most frequently during the expansion of referral ties and contacts in the early phase of transition.
- (5) During the course of coaching, families' networks will move from more professional, health services support to more community, educational and peer support.

RESEARCH METHODS

The developmental coach model proposes a partnership with families in the redesign of care that fosters knowledge exchange and a supportive learning environment. The coach will provide knowledge about child development, support to foster parent empowerment and guidance on navigation of the health care system. Web-based tools on healthy development and a peer support network using an online platform (Igloo - see below) complement the coach's role. Participants will be randomized to either our BRIGHT systems model which includes usual care, or usual care alone, and tracked over time. The selected target population represents a group vulnerable to poor access to care and misuse (both overuse and underuse) of specialized developmental services in the preschool years, prior to school entry. This group provide a unique opportunity to understand how to best optimize child and family well-being.

Trial design:

This is a prospective, two-arm pragmatic randomized controlled trial (RCT) comparing a developmental coaching and e-health services intervention plus usual care to the control state in which children and their families receive usual care over a 12-month time frame. The target population for this novel service delivery model is preschoolers at high risk for or suspected of having developmental delays, that are beginning to manifest impairments in developmental domains (e.g. motor, cognitive, speech, social and/or behavioural). In the first year, a technology-supported health coach service delivery model will be developed in conjunction with families. A feasibility/acceptability pilot study will be conducted to ensure that the intervention can be done in the real life context across 4 provinces. Fidelity of the coach will be verified by the master trainers (AM and MO). After modifications to enhance feasibility, the RCT will follow.

Participants:

Eligible children and their families will be recruited to include preschool children 1.5-4.5 years (18 to 54 months) at the age of enrolment, who are not expected to enter school/kindergarten within 6 months of enrolment. Children will be living in four diverse parts of Canada to ensure national representation and future scalability: British Columbia, Manitoba, Nova Scotia, Quebec. Participants' postal codes will be analyzed to ensure representation: rural/remote, small urban and large urban/metro representation with purposeful sampling as required. From the patient population perspective, two different groups that are likely to manifest new global developmental delays at this stage will be recruited. They are at high risk for brain-based developmental delays, however some will have no delay and others will have mild, moderate or severe delays.

Children at risk who are not yet receiving developmental services: Primary care provider and/or parental concerns regarding their child's developmental progress become apparent in the preschool years.

Inconsistent use of screening tools and variation in triage and assessment methods often result in delayed detection and long wait lists for services. Children will be those waiting for their first formal appointment for diagnosis and assessment for “developmental delay”, from a public health facility, a child developmental centre and/or a dedicated hospital clinic. These children represent a group who are not currently receiving developmental services. These children may be found to have no delay, a delay in one domain (e.g. specific language impairment) or global delays, which can be mild to severe. This will be a consecutive sample on the wait list and who are between 1.5-4.5 years of age.

For this trial, children/families will be excluded if they: (1) are non-English speaking (and non-French speaking in sites where services are available in French); (2) are unwilling or unable to meet with the study team for intermittent assessments; (3) do not have access on a routine basis to the internet through a desktop or mobile device. We will recruit 350 subjects, 175 for both intervention and control arms.

Study procedures: Intervention and control

Recruitment will begin with family contact. Each site manages their own recruitment process and protocol. Please see our *Recruitment Protocol* in Montreal (Appendix). Families will be contacted via the centre to which they were referred for developmental diagnosis and assessment. A member of the clinical team will ask if they are interested to learn more about the BRIGHT Coaching study. If interested, the families' contact information will be shared with the local research assistant (RA) overseeing the trial. The RA will speak to a parent by phone and follow up with an introductory letter by mail and/or email explaining the procedures of the study, together with the consent form. After 1 to 10 days, the RA will call the family to determine interest in participating and answer any questions. If interested in participating, parent can either 1) sign the consent form and scan by email to the RA, 2) send the consent form to the RA by mail/ hand it to them in person, 3) agree to a verbal consent process and verbal consent will be given to the RA over the phone (in accordance with the Tri-Council Policy Statement on verbal consent). Once consent is signed, participants will conduct baseline assessments including documentation of their care and social networks, and be randomized using a computer-generated algorithm; randomization will be stratified by site. The allocation ratio for intervention or control will be 1:1 for each site.

The developmental coaching intervention will be developed in year 1. A coaching consensus workshop took place in Vancouver for August 20, 2016, and focussed on the “key ingredients” for a coach model. This workshop will be followed by team meetings (with relevant stakeholders) in order to develop a standardized manual to include definition of roles and functions and ‘active ingredients’ to successful coaching. A standardized approach to coaching will be developed guided by the participation of families (our parent advisory group) and using the best evidence. The responsibilities of the coach are expected to include: i) helping families identify areas of developmental concerns (e.g. using the checklist of developmental milestones published by Centre of Disease Control & Prevention), ii) proactive health promotion and guidance with respect to developmental stimulation and skills training to optimize development, iii) parent education about child development consistent with the child’s current strengths and challenges and the parents’ areas of greatest concern, iv) parent support, v) provision of general information regarding the general developmental services that might be of benefit to the child (e.g. seeing an audiologist or neurologist). The coach at each site will have skills in family support, and expertise in child development; but will not be a registered health professional (for real-life generalizability and cost). The coach will possess skills such as motivational interviewing techniques, individual and collaborative goal-setting and shared decision-making. There will be a minimum frequency defined as one telephone contact

2-4 times per month for 45-60 min for each session, and the duration of contact will be 12 months. Instructions for specific coaching situations will be created based on the assumptions that (1) parents have similar self-management skills and needs, (2) parents can develop skills in supporting their child's development and accessing services, (3) confident, knowledgeable parents will support their children in accessing services that are appropriate and utilize fewer health/social resources if they are more supported in determining the direction to which they should go.

The intervention will be provided in a flexible manner, as determined by the parents' needs, circumstances and preferences and the child's developmental condition. Mothers and fathers will both be encouraged to interact with the coach and seek advice and support. The coach will be reachable at least every second day (minimum 4-6 hours per day, 3 days per week); however, calls with families will vary from a minimum of every 4 weeks (ideally every 2 weeks) and will be scheduled at a time convenient for the parent with evening appointments available until 8 pm at least one night per week. Calls will be audiotaped and reviewed by the study team to ensure program quality and reviewed by peer-coaches for self-review and program quality improvement on an iterative basis. Coaches will receive manuals and specific training activities including small group discussions, experiential learning and sharing of best practices among coaches in the trial. A registered health professional (i.e. experienced social worker and family counsellor with expertise in family/ young child counselling) has been hired as a "Coach Lead" to provide training, mentoring and oversight of coach activities.

In addition to the coach, specific evidence-based *educational web content* will be sourced and curated by the project team and relevant stakeholders (conducted in the first year as part of intervention development). Input and feedback from the parent advisory group will further refine and inform the program content. The content will be linked to an online care coordination platform - the *Igloo platform* - which puts each family at the centre of each network (family, friends, health professionals), and then allows each family network to link with other family networks in the intervention arm of the study. This will enable families the opportunity to find and store resources, create connections with the coach, health providers and other families, thereby creating a network of individuals to support them formally and informally. Peer support (among parents in the intervention arm) will be a critical part of this service delivery strategy, enabling parents to share strategies. This password-protected website will include credible links to sites based on the family-based needs assessment described above.

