Once past the feasibility stage, outcomes will be measured at 8 months and 12 months after recruitment. The primary outcome of interest in the RCT is the *parents' ability to self-manage and promote their child's development*. Thus, the primary outcome measure is the Family Empowerment Scale, which focuses on empowerment at the family (managing the day to day), services (working with system to receive adequate services) and community (finding or advocating for needed supports, policies, agencies) levels [13]. Its psychometric properties are acceptable. A second measure will be the Parents' Sense of Competence Scale which measures satisfaction (anxiety, motivation, frustration) and efficacy (capability, problem-solving) with parental roles [14].

Secondary measures of intervention efficacy apply the Triple Aim Framework and will include:

1. Parental well-being: SF-36 [15] (quality of life) and the Parenting Stress Index [12] (parent stress level).
2. Family health care experience: Measure of Process of Care [16] (the extent to which care is family-centred)

3. Health care costs/ service utilization patterns: the Resource Utilization Questionnaire (adapted from Drs. [name] and [name]) uses standardized metrics for the evaluation of costs (health care and out-of-pocket), consequences and benefits from the patient, provider and health system perspectives.
4. Care and social networks: Care and social networks will be tracked using Igloo analytics. This will include tracking during the transition from preschool to school-aged services and the identification of professional and community supports.
5. Engagement of mothers and fathers with BRIGHT program: Analysis of electronic contact data from Igloo platform by mothers and fathers (gender).

Exploratory measures will include:

Child's functional abilities and independence: Vineland – daily living skills, socialization, etc .. Importantly, in the spring of 2017, an online “needs assessment” survey was conducted with Canadian families to influence the content of the coach intervention and to determine the outcomes of greatest interest to families and administrators.

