Descriptive statistics will be used to characterize our sample in the experimental and control arms. The primary analysis is to ascertain benefit of the BRIGHT system (Coach + online education tools + online peer support) compared to usual care (control) will be between group (intervention vs control) comparison of primary and secondary outcomes using t tests (two-sided, $p<.05$). Statistical comparisons will be made at 8- and 12- months post enrolment, to determine if group differences manifest early and if they continue to improve or stabilize. This will be important in determining whether the BRIGHT system is necessary over a prolonged period (8 vs 12 months) to achieve its goals. Principles of intent-to-treat analysis will be applied. Repeated measures with mixed model analysis will be used to assess effect of group category and province with intervention at two time points. Within the intervention group, predictors of change scores between baseline and outcomes (dependent variable) will be tested to determine which children/families are more likely to be responsive to the BRIGHT system. Multivariate linear regressions will be conducted with independent variables, to include: parent readiness score, sociodemographic factors, child's functioning (Vineland), province, and engagement in the Igloo platform. The structural properties of the network (Igloo) will be analysed using UCINET [17]. Network analysis related to patterns of use of the online platform will be correlated with the outcome measures of interest in this study.

Sample size:

We will recruit 392 participants; we project a sample size of 352 based on: i) two-sided test of the null hypothesis at $\alpha=.05$, ii) $\beta=.80$, iii) 10% attrition; iv) difference of 0.3 SD.

Studies as of yet have not identified a minimal clinically important difference (MCID) for our primary outcome measure (the Family Empowerment Scale) that could be used to estimate sample size calculation. In the absence of a “clinimetric” MCID, a distribution-based methods approach is commonly applied that proposes a fraction of the pooled Standard Deviation (i.e. utilize effect size estimates). In this case, the difference of 0.3 standard deviation can be used to detect modest effects that may be clinically significant; or 0.5 SD for moderate to large effects [18, 19].

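### Primary Hypothesis 2 claims similar health care cost, but the only decision rule that covers cost is a two-sided difference test, which cannot support similarity

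*Protocol*

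**What the plan says.** Under Aims and Hypotheses, Primary Hypothesis 2 states that coaching improves parental health and family care experience "at similar *health care cost* (economic analysis), when compared to usual care". The cost clause is therefore a similarity claim inside a primary hypothesis.

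In the section on data collection and outcome measures, cost is item 3 of the list that opens "Secondary measures of intervention efficacy apply the Triple Aim Framework and will include": "Health care costs/ service utilization patterns: the Resource Utilization Questionnaire". Table 2 also places it among the secondary outcomes. The questionnaire is said to be one that "uses standardized metrics for the evaluation of costs (health care and out-of-pocket), consequences and benefits from the patient, provider and health system perspectives".

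The Statistical analyses section sets the between-group analysis as a "comparison of primary and secondary outcomes using t tests", two-sided at p<.05, at 8 and 12 months. It adds a mixed model: "Repeated measures with mixed model analysis will be used to assess effect of group category and province with intervention at two time points". No margin, interval criterion or definition of similar cost is attached to either.

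Two other statements bear on cost. The plans for knowledge translation list a cost-utility analysis as content for policy-makers, without a rule. The opening summary expects that the resulting service models "will be associated with cost-savings to the system and patient/family benefits to health and well-being", which is a different claim from similar cost.

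**The concern.** A two-sided t test asks whether the data contradict equal means. A significant result would count against similar cost. A non-significant result says only that a difference was not shown. Under the stated rule, then, no outcome of the test is positive evidence for the cost clause of Hypothesis 2.

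Coaching and the online platform are delivered on top of usual care, so a real cost increase is possible. Cost data also tend to vary widely, which widens the interval for the difference. The cost result is meant to feed a policy dialogue and briefing notes for provincial ministries. If the cost clause were taken as met because the test was non-significant, that message could rest on imprecision.

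**Working it through.** **1. The plan's own figure.** The Sample size section gives 352 analysed and 392 recruited, for a difference of 0.3 SD, two-sided alpha .05, power .80 and 10% attrition.

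- Normal approximation: n per arm = 2 × (1.96 + 0.8416)² / 0.3² = 174.4, so 175.
- t-test calculation: 175.4, so 176 per arm, or 352 in total. 352 / 0.9 = 391.1, so 392 with equal arms.

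The figure reproduces. It is a superiority size, argued for the Family Empowerment Scale and not for cost.

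**2. Inputs for cost.** The protocol gives both 350 recruited (Participants) and 392 recruited (Sample size).

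- 350 × 0.9 = 315 evaluable, or 157.5 per arm.
- 352 evaluable, or 176 per arm.
- CV of cost (SD divided by mean): not in the protocol. Assumed 1 to 2, equal in both arms.
- True increases of 20% and 30% of mean cost: chosen for illustration. The protocol does not say what increase would matter.

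**3. Precision.** As a fraction of mean cost, SE = CV × √(2 / n per arm), and the 95% half-width = 1.96 × SE.

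- 157.5 per arm: SE = 0.1127 × CV, half-width = 0.221 × CV.
- 176 per arm: SE = 0.1066 × CV, half-width = 0.209 × CV.

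**4. Chance that a real increase is non-significant.** With true increase d as a fraction of mean cost, this is Φ(1.96 − d/SE) − Φ(−1.96 − d/SE). Example at CV 1, d = 0.20, 157.5 per arm: d/SE = 1.775, and Φ(0.185) ≈ 0.57.

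| CV (assumed) | Half-width, 315 evaluable | Half-width, 352 evaluable | True +20% missed (315) | True +30% missed (315) |
|---|---|---|---|---|
| 1 | 22% | 21% | 57% | 24% |
| 1.5 | 33% | 31% | 78% | 57% |
| 2 | 44% | 42% | 86% | 73% |

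The choice between the two sample sizes hardly matters. In SD units with 176 per arm, a true difference of 0.1, 0.2 or 0.3 SD is non-significant about 85%, 53% or 20% of the time.

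**5. What the same data could show against a margin.** Take 176 per arm, no true difference, SE = 0.1066 SD and margin m in SD of cost. Equivalence power = 2Φ(m/SE − z) − 1, or 0 if that is negative.

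| Margin m | 90% interval (two one-sided tests at .05, z = 1.645) | 95% interval (z = 1.96) |
|---|---|---|
| 0.2 SD | 18% | 0% |
| 0.3 SD | 76% | 61% |
| 0.5 SD | 99.8% | 99% |

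For 80% power with the 90% interval, 429 per arm would be needed at 0.2 SD and 191 at 0.3 SD. If the CV is 1 to 2, a margin of 0.3 SD is 30% to 60% of mean cost.

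**The case against.** The strongest reply is that cost has its own method. Hypothesis 2 names an economic analysis in brackets, the research question mentions cost-effectiveness, and the questionnaire is described in terms of costs and consequences. The t-test sentence gives its purpose as establishing benefit, and similar cost is not a benefit. An economic evaluation would normally report an incremental cost, and its detail may sit in a separate plan. This stands in part: the absence of bootstrap or skewness detail from the protocol is no fault. But the t-test sentence expressly covers secondary outcomes, cost is listed as one, and none of the economic terms comes with a criterion. A later plan that follows the protocol would inherit the mismatch.

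Three stronger readings are tempting, and the document does not support them.

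- A reader might infer that the sponsor will treat p>.05 as proof of similarity. No sentence says so; the hypothesis and the rule only leave that open.
- A reader might infer that the trial is too small to show similar cost. The limit lies in the rule, not in the trial: at a margin of 0.3 SD the power is far from negligible, and at 0.5 SD it is nearly complete.
- A reader might infer that non-significance is the likely result whenever cost rises materially. At CV 1 a true 30% increase would be missed only 24% of the time, and the protocol does not define a material increase.

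The cost-savings phrase in the opening summary is an aspiration for future service models, not a decision rule, so it is a matter of wording only.

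**Conclusion.** The point holds as a mismatch between hypothesis and test. The protocol makes similar cost part of a primary hypothesis, and the only between-group decision rule it states for that outcome can refute similarity but never support it. A non-significant result would be compatible with a sizeable cost increase, given the interval widths above. Those widths rest on the assumed CV of 1 to 2, equal variability in the two arms and a normal approximation for the difference in means. The logical point needs none of these.

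The change should be made, but its reach is limited. Cost is one clause of a hypothesis with several parts and is secondary in both outcome lists. The conclusion on the Family Empowerment Scale, the sample size and the data collection are untouched.

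**What to change.** In the Statistical analyses section, take cost out of the blanket t-test sentence. State that the mean cost difference between arms will be reported with a 95% confidence interval (for example by bootstrap, since costs are usually skewed) as part of the economic analysis. Then choose one of two routes:

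- **Keep the similarity claim.** Agree and justify a cost margin before outcome data are seen. Conclude similar cost only if the interval lies wholly within it, and otherwise call the result inconclusive. Fix the interval level for this decision at the same time, because the 90% and 95% intervals differ in power. The sponsor should know that a margin of 0.2 SD or tighter is out of reach at the planned size.
- **Drop it.** Reword the cost clause of Hypothesis 2 as estimation of the incremental cost.

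In either case, state that p>.05 is not evidence of similar cost, and align the cost-savings wording in the opening summary with the hypothesis.

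The cost is a few sentences and, on the first route, one agreed margin. No new data are needed. The downside is that the cost conclusion may have to be reported as inconclusive.
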